- 3. A score of 20 or more on the Adult ADHD Investigator Symptom Report Scale (AISRS), and, for those individuals stably treated with stimulants, a CGI-ADHD severity score of no greater than 4 ("moderately ill").
 - i. Subjects on a stable dose of stimulant medication must be treated on the same dose for at least 1 month prior to study entry.

Exclusion Criteria:

- 1. A history of intolerance to magnesium supplementation, or the ingredients in MMFS202 (6-hour release) AND MMFS302 (12-hour release).
- 2. Pregnant or nursing females.
- 3. A known unstable medical illness including hepatic, renal, gastroenterological, respiratory, cardiovascular (including hypertension ≥ 140/90 mmHg at screening), endocrinologic (e.g. thyroid), neurologic (e.g. seizure), immunologic, hematologic, or psychiatric (other than ADHD) disorder. Individuals with kidney dysfunction will be excluded, as dysfunctional kidneys may have difficulty clearing the magnesium from the body (which can result in dangerously high magnesium levels). Individuals with heart block will be excluded from the study.
- 4. Any medical condition that the Principal Investigator (PI) believes will be exacerbated by study participation.
- 5. A history of cancer (except localized skin cancer without metastases or *in situ* cervical cancer) within 5 years prior to screening.
- 6. A known history of narrow-angle glaucoma.
- 7. Current (within 3 months) DSM-V criteria for abuse or dependence with any psychoactive substance other than nicotine.
- 8. IQ<80 (based on the Wechsler Abbreviated Scale of Intelligence-II Full Scale IQ calculation)
- 9. Multiple adverse drug reactions.
- 10. Any other concomitant medication with primarily central nervous system activity as specified in Concomitant Medication portion of the protocol.
- 11. Current use of MAO Inhibitor or use within the past two weeks.
- 12. Current use of antibiotics, as the study agent may reduce the absorption of antibiotics.
- 13. Subjects may not take any of the following substances for at least 7 days prior to baseline and throughout the study:
 - a. Calcium channel blockers including:
 - i. Felodipine (Plendil®)
 - ii. Amlodipine besylate (Norvasc®).
 - b. Any psychoactive medications including:
 - i. Antipsychotics
 - ii. Anxiolytics
 - iii. Antidepressants
 - c. Any medications known to interact with magnesium including:

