 - i. Potassium-sparing diuretics such as Amiloride (Midamor), Spironolactone (Aldactone®), and triamterene (Dyrenium®), as they may increase magnesium levels;
 - ii. Loop and thiazide diuretics such as Furosemide (Lasix®) and Hydrodiuril (Microzide ®, Esidrix®, Hydrodiuril®) as they may decrease magnesium levels;

- iii. Muscle relaxants such as Carisoprodol (Soma®), Pipecuronium (Arduan®), Orphenadrine (Banflex®, Disipal®, Norflex ®), Cyclobenzaprine (Flexeril®, Fexmid®, Amrix ®), Gallamine (Flaxedil®), Atracurium (Tracrium®), Pancuronium (Pavulon®), and Succinylcholine (Anectine ®, Quelicin®);
- iv. Penicillamine (Cuprimine®, Depen ®)
- v. Corticosteroids (Prednisone or Deltasone®)
- vi. Magnesium containing antacids including Maalox®, Mylanta®, Milk of Magnesia, Tums® and Rolaids
- d. Supplemental magnesium or any magnesium-containing products
- e. All dietary or herbal supplements or products including those purported to improve memory, improve sleep, or decrease stress.

Any subject found to be taking these substances during the study will be evaluated by the PI for ongoing eligibility.

14. Investigator and his/her immediate family; defined as the investigator's spouse, parent, child, grandparent, or grandchild.

There will be two categories of individuals presenting with ADHD that will participate in the study: (1) those that have residual ADHD symptoms despite benefit from well-tolerated standard of care ADHD pharmacotherapy (stimulant medication or Atomoxetine); and (2) those that are not on medication for ADHD. Because the study is a pilot study, we will recruit a sample of subjects, and have not specified a ratio of participants in these two groups to be enrolled.

No individual will be removed from an effective and stable treatment regimen for the purposes of participating in the study. Individuals who enter the study on medication for ADHD must be on an effective, well tolerated, and stable dose of a prescription indicated by the FDA for ADHD for at least one month prior to entry. Efficacy and tolerability will be determined by the study clinician, and subjects must have a Clinical Global Impression-ADHD severity rating of no greater than 4 ("moderately ill"), because a score greater than 4 indicates that their ADHD symptoms are unlikely to be effectively treated by their current medication regimen.

IV. SUBJECT ENROLLMENT

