We anticipate that subjects may enter this trial following completion of withdrawal from other protocols in our office, and that there may be procedural overlap. So as to not burden subjects with redundant time commitments, we will use the following *diagnostic* data previously collected: If a subject has completed an evaluation with one of the study clinicians within the previous year prior to entrance into this study, they will not be asked to repeat any overlapping diagnostic procedures; if a subject has completed a neuropsychological evaluation within the last 3 months they will not have to repeat this. With subjects' permission, we will use the diagnostic data that had been previously collected. However, the study clinician will review the interval time period to assess for clinically significant medical or psychiatric history, to ensure that the subject meets appropriate study entrance criteria.

Medication Washout:

If clinically appropriate, any subjects taking medication exclusionary to the study must be tapered off this medication prior to baseline visit for the length of 5 half-lives of the medication, corresponding to 95% of the agent leaving the participant's system), plus several days to assess the participant off medication. Discontinuation or taper off of a current medication will be recommended only for subjects with inadequate response to a current treatment. Subjects will not enter the study if it would require tapering a medication that is optimally and comfortably managing a clinical concern. Medication tapers will be monitored by the study clinician in agreement with the research subject and in consultation with the prescribing physician. The prescribing physician will be contacted to discuss feasibility and correctness of removing a subject from current medications and will be asked to monitor the subject's response to the medication change. If the prescribing physician does not find medication discontinuation appropriate or if they do not agree to monitor the subject's response to stopping medications, then the subject will not be enrolled. No subject will be removed from a stable and effective treatment regimen for the purposes of participating in the study.

Participants who fulfill the inclusion and exclusion criteria will participate for 12 weeks, or until withdrawing or terminating participation.

Safety Assessments:

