Study clinicians, or research assistants under the supervision of a study clinician, will be responsible for dispensing MMFS302 (12-hour release) and MMFS202 (6-hour release) at our research office. The MGH Clinical Trials Pharmacy will receive and label and distribute the product for dispensing during the study.

Study clinicians, in cooperation with the subject and the subject's treater, may develop a plan for continued MMF302 (12-hour release) and MMF202 (6-hour release) treatment after the completion of the study, if appropriate. At each visit, measures of safety and effectiveness will be administered and subjects will be evaluated for response and side effects to the treatment. To assess and increase adherence to dosing of the agent, the study agent and any concurrent ADHD medication treatment will be returned and counted at office visits.

Concomitant Medications / Treatments:

A detailed past and present treatment history will be taken as part of initial screening. Concomitant medications with primarily central nervous system activity, other than ADHD pharmacotherapy as noted above, are not allowed in this study. No subject will be tapered from medication that is useful to him or her. Non-pharmacological treatments such as individual, family or group therapy will be allowed if they were in place before the patient joined the study. Any such therapy regimen must remain the same throughout the study. If a subject is asked to stop a medication with central nervous system activity for participation in the study, sufficient time will pass off the medication prior to baseline visit, based on the pharmacokinetics of the agent, to ensure that it has been eliminated from the patient's system.

Subjects will be instructed not to take any medications or supplements that contain any forms of magnesium compounds to avoid unsafe levels of magnesium. All new medications and supplements started during the study will be reviewed by the PI, and subjects may be dropped from study participation, but their data will be retained in the safety and intent-to-treat analyses with PI discretion.

In addition, any subject found to be taking medication listed as exclusionary during the course of the study or the seven days prior to baseline will be evaluated by the PI for ongoing eligibility.

Study Discontinuation Criteria

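### The one-month stability rule covers only subjects continuing ADHD medication; newly started therapy and an ADHD drug stopped independently before entry have no stated stability period in a single-arm pre-post study

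*Combined protocol and SAP*

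**What the plan says.** Section III (Subject Selection) admits two kinds of subject. Those who continue ADHD pharmacotherapy must be on a "stable dose of a prescription indicated by the FDA for ADHD for at least one month prior to entry". Inclusion criterion 3 repeats the rule, but for stimulants only: "Subjects on a stable dose of stimulant medication must be treated on the same dose for at least 1 month prior to study entry". The second kind is "2) those that are not on medication for ADHD", with no time since the last ADHD drug attached.

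Section V (Study Procedures, Concomitant Medications / Treatments) says that non-pharmacological treatments such as psychotherapy "will be allowed if they were in place before the patient joined the study". They must then stay the same during the study. No minimum duration before entry is given.

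Section III allows entry after an earlier medication trial in the program. Section V, just before Medication Washout, anticipates that "subjects may enter this trial following completion of withdrawal from other protocols in our office". Neither place states a gap.

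The plan does regulate some stopped drugs. Under Medication Washout, a subject taking exclusionary medication must be "tapered off this medication prior to baseline visit for the length of 5 half-lives of the medication", "plus several days to assess the participant off medication". Stopping "will be recommended only for subjects with inadequate response to a current treatment". Concomitant Medications / Treatments requires elimination time, based on pharmacokinetics, for a centrally acting drug that the subject is asked to stop. Exclusion criterion 13 sets 7 days for a list of substances.

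Section VI (Biostatistical Analysis) describes a single open arm of 15. AISRS, BRIEF and CANTAB are compared with pre-treatment values by paired t-test. There are also individual thresholds: a 25% fall in AISRS total, a CGI rating of much or very much improved, and a 0.5 SD improvement on BRIEF-A.

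**The concern.** With no control arm, a settled baseline is the main design protection against change that was already under way. The plan recognises this for continuing medication users by asking for a month on the same dose. It does not ask the same of two other groups whose treatment may have changed just before baseline.

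The first group has newly begun therapy. Any benefit still building over the 12 weeks enters the AISRS, CGI and BRIEF-A results and cannot be separated from the agent.

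The second group has recently come off an ADHD drug without being asked to by this study. Section VII (Washout) itself accepts that symptoms may worsen when medication stops. Such a baseline could be temporarily high, or still held down by residual benefit.

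The pilot is meant to guide a later double-blind study, so a distorted estimate of change would be carried into that design.

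**Working it through.** **Which rule applies to whom**

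| Situation before baseline | Where addressed | Interval stated |
|---|---|---|
| Continuing an ADHD drug | III, inclusion 3 and the text on the two categories | one month, stable dose |
| Taking an exclusionary drug | V, Medication Washout | 5 half-lives plus several days |
| Asked to stop a centrally acting drug | V, Concomitant Medications / Treatments | elimination time, no number |
| Substances listed in exclusion 13 | III | 7 days |
| Stopped an ADHD drug independently | no rule clearly applies | none |
| Just left another protocol in the program | III and V, as a source of subjects | none |
| In psychotherapy | V, Concomitant Medications / Treatments | none; must only predate entry |

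Three steps show why the fifth and sixth rows stay open.

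1. The 5-half-life rule is for subjects taking exclusionary medication. Stimulants and atomoxetine are permitted, and a person who has already stopped is no longer taking them.
2. The elimination-time rule is triggered by a request to stop for this study. It does not describe someone who stopped for other reasons or left another trial.
3. Exclusion 13 lists psychoactive drugs as a class and applies for 7 days before baseline and throughout the study. If that included ADHD drugs, it would bar every subject who continues one, so it cannot sensibly be read that way.

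The first two rules, where they apply, aim mainly at drug elimination. None of the three sets a period of symptom stability.

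**Scale (illustration only)**

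The documents give no SD, effect size or count of such subjects, so there is no plan figure to reproduce. From the plan: n = 15, alpha = 0.05, AISRS entry floor 20, response threshold 25%. Assumed: k = 2 to 5 affected subjects, each changing by d = 5 to 8 AISRS points for reasons unrelated to the agent; SD of change 6 to 10; two-sided test.

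Shift in mean change = k × d / 15:

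- smallest: 2 × 5 / 15 = 0.67 points
- middle: 3 × 5 / 15 = 1.00 point
- largest: 5 × 8 / 15 = 2.67 points

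Chance of a significant result when the agent does nothing (200,000 simulated trials per row, normal changes, paired t-test):

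| SD | k | Change per affected subject | Significant improvement | Significant worsening |
|---|---|---|---|---|
| 8 | 0 | none | 2.5% | 2.5% |
| 10 | 2 | 5 points better | about 4% | 1.3% |
| 8 | 3 | 5 points better | 5.8% | 0.7% |
| 8 | 5 | 8 points better | 16.8% | 0.04% |
| 6 | 5 | 8 points better | 23.4% | 0.01% |
| 8 | 3 | 5 points worse | 0.7% | 5.8% |

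For one subject at the entry floor, 0.25 × 20 = 5, so a 5-point improvement from another cause meets the AISRS criterion by itself.

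**The case against.** The strongest reply is that the plan does control recent stopping. A reader might infer that anyone who has just come off an ADHD drug can enter at once. The documents do not support that: a drug stopped for the study needs elimination time, and an exclusionary one needs 5 half-lives plus several days. This part of the reply stands, and it limits the drug half of the point to independent stoppers and people leaving other protocols.

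A reader might also see a loophole for a medicated subject with CGI severity above 4, who could stop the drug and enter as unmedicated, where no cap applies. That is not an unguarded route. Medication Washout limits stopping to inadequate response, requires the prescriber to agree and to monitor, and provides for assessment off the drug. The cap tests whether the current drug is working, so its absence for untreated subjects is logical.

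It can further be said that this is an exploratory pilot on tolerability and feasibility, and that no entry rule would remove expectancy or natural change. That is true and limits the weight of the point. It does not explain why a protection that the plan thought worth having for one group is missing for the others.

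Finally, a month of unchanged therapy does not guarantee that its benefit has levelled off. That is also fair; the window reduces the problem and makes the groups consistent, but does not abolish it.

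**Conclusion.** The gap is real but narrow. For therapy it is plain on the text: a course begun just before baseline qualifies, and any benefit still building would favour the agent. For ADHD drugs it is a gap in coverage and clarity: no interval is stated for unmedicated entrants, and the washout rules do not clearly reach those who stopped independently or came from another protocol.

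A reader might infer that all such change is credited to the agent. For recent stoppers that does not follow. Recovery from a transient worsening would flatter the agent, while continued loss of drug benefit would count against it. The right description is confounding in either direction.

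The size is unknown, because the plan gives neither the number of such subjects nor a ratio between the two categories. The shift of 0.67 to 2.67 AISRS points, and the rise in false improvement from 2.5% to between about 4% and 23%, rest wholly on the assumed counts, changes and SDs. The correction is worth making because it is cheap. It does not show that the study's result will be wrong.

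**What to change.** 1. In section V, Concomitant Medications / Treatments, replace the condition that therapy merely predates entry with therapy unchanged for at least one month before baseline. This matches the plan's own window for medicated subjects and is an entry condition only.
2. Record the therapy start date and the date of the last ADHD drug at eligibility. In section VI, add that AISRS, CGI and BRIEF-A results will be reported with and without subjects whose treatment changed in the month before baseline.
3. Reconcile inclusion criterion 3, exclusion criterion 13, the text on the two categories, Medication Washout, and Concomitant Medications / Treatments. They should say whether and how the stability and washout rules apply to a subject who recently stopped an ADHD drug, including one arriving from another protocol. The interval is for the investigators to set; none is proposed here.

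The cost is a few sentences, two dates on the eligibility form and one small sensitivity analysis. A few candidates in new therapy would start up to a month later.

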Vital signs (blood pressure, pulse, weight) will be measured at every in-office visit. Height will be measured at baseline and at the end of the study. A urine drug screen will be performed at screening, week 6, and week 12. If the participant is found to have taken an illicit drug, he/she will have a discussion with the doctor to determine if he/she can be in the study. Subjects will be discontinued if there is suspicion of ongoing substance use. For safety purposes, an EKG will be conducted during screening and at the endpoint of the study. Females who are able to have children will also have a urine pregnancy test at screening, week 6, and week 12.

If a participant has a positive pregnancy test she will not be able to take part in the study. Female subjects of childbearing potential must agree to use a medically acceptable form of birth control (such as male for female condoms with or without spermicidal agent, diaphragm or cervical cap with spermicide, medically prescribed IUD, hormonal contraceptives like birth control pills, or abstinence) while they are receiving study agent and for 1 month after the last dose of study agent. In the event that a subject becomes pregnant, we will ask the subject's permission to obtain information about the outcome of the pregnancy and the condition of the newborn. Those subjects who terminate study participation before the completion of the study will be asked to complete all tasks scheduled to take place on the final study visit at the time of study discontinuation.

We will draw blood samples at the screening visit and at study endpoint to determine erythrocyte (red blood cell or RBC) levels of magnesium and calcium. Samples will be analyzed by LabCorp through services provided by the Harvard Clinical and Translational Science Center. Each sample volume will be approximately 3 teaspoons, for a total of 6 teaspoons drawn over the entire study.

All efforts will be made to protect subject privacy, and samples will be labeled with codenames and medical record numbers. The sponsor will not have access to information that identifies participants' samples. Results from laboratory testing (i.e. laboratory values) may become a part of the subjects' MGH medical records, however no information regarding participation in the study will become a part of the medical record.

Subject Visits:

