concerning trends in participants' experience that would require discontinuation of study participation or modification of the protocol. The Principal Investigator will confirm that all adverse events are correctly entered into the adverse event log by the coordinator and will be available to answer any questions that the coordinators may have concerning adverse events and notifying the IRB of all serious adverse events and adverse events in accordance with the guidelines outlined on the Partners Human Research Committee web site.

The Principal Investigator will meet regularly with study staff to address procedural issues and the study coordinator will audit each subject's data within 48 hours of each study visit. Furthermore, all data will be audited by the study statistician on a regular basis to ensure the progress of the study and confirm that all necessary data is being collected and can be transitioned to the statistical package smoothly. Co-investigators are actively involved in the monitoring and quality assurance of these trials. Periodic quality assurance audits will insure accuracy and completeness of all subject documents, IRB files and correspondence, and the informed consent documentation.

	Screen	Baseline (Week 0)	Week 1	Week 2	Week 3	Week 4	Week 5	Week 6	Week 7	Week 8	Week 9	Week 10	Week 11	Week 12 (Drop)
Consent	Х													
Eligibility	Х	X ^a												
Procedures														
Blood Pressure	Х	Х			Х			Х			Х			Х
Pulse	Х	X X			X			X X			Х			Х
Weight	Х	Х			Х			Х			Х			Х
EKG	Х													Х
Height	Х													X
RBC Mg and Calcium	Х													Х
Urine Drug	Х							Х						Х
Urine Pregnancy	X							Х						Х
Drug accountability		X ^b			Х			Х			Х			Х
Drug Dispensing		Х			Х			Х			Х			
Phone Contact			X ^c	Х		Х	Х		Х	Х		X	X	
Assessments														
Demographic Interview	Х													
WASI-II	Xd	Xď												Х
D-KEFS Trails	X ^d	X ^d						Х						Х

VIII. Visual Timeline of Key Study Elements

CANTAB	X ^d	Xď				X					Х
Clinician Evaluation	X										
Clinician Rated Scales											
AISRS	Х	Х		Х		X		X			Х
CGIs	Х	Х		X		Х		X			Х
GAF		Х		X		Х		X			Х
Adverse Events			Х	X		X		X			X
Concomitant Medications	X	Х		X		X		X			Х
Subject Rated Scales											
BRIEF-A		Х									Х
ASRS		Х		X		Х		X			Х
ASR		Х									Х
Q-LES-Q		Х									Х
EWPS		Х									Х

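### No pregnancy test is scheduled at baseline, when the study agent is first dispensed, and contraception is not required between screening and first dose

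*Combined protocol and SAP*

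**What the plan says.** Under Safety Assessments in Section V, the schedule is: "Females who are able to have children will also have a urine pregnancy test at screening, week 6, and week 12". The "Urine Pregnancy" row of the Visual Timeline of Key Study Elements carries three marks, consistent with those visits. The "Drug Dispensing" row starts at baseline and continues at weeks 3, 6 and 9.

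Exclusion criterion 2 reads "Pregnant or nursing females", and Safety Assessments adds: "If a participant has a positive pregnancy test she will not be able to take part in the study". The Study Discontinuation Criteria also end participation for anyone who becomes, or intends to become, pregnant.

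Contraception is required "while they are receiving study agent and for 1 month after the last dose of study agent".

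Timeline footnote (a) says that eligibility is confirmed at baseline but names no test. Footnote (d), which lets a procedure fall at either screening or baseline, is attached only to the WASI-II, D-KEFS and CANTAB rows.

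**The concern.** The only pregnancy test before dosing is at screening, and nothing limits how old that result may be when the agent is handed out. The plan does set age limits for other entry data that are reused (one year for the diagnostic evaluation, three months for neuropsychological testing), but none for this test. The timings it does give before baseline are minimums, and they lengthen the gap for anyone who has to stop something after screening.

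The contraception requirement does not cover the gap either. A woman who starts contraception on the day of her first dose complies fully, yet may have conceived since screening.

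What is at stake is avoidable fetal exposure. The exclusion criterion itself is sound, but the schedule does not verify it at first exposure. No endpoint or analysis depends on this.

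**Working it through.** The plan gives no figure to reproduce, so the check sets the provisions side by side and then bounds the size.

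**Sequence of events**

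| Step | Agent dispensed | Pregnancy test |
|---|---|---|
| Screening | No | Yes |
| Baseline (week 0) | Yes, first time | No |
| Week 3 | Yes | No |
| Week 6 | Yes | Yes |
| Week 12 | No | Yes |

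Two dispensings precede the first on-treatment test. Write S for the screening-to-baseline interval in days. Consecutive tests are then S + 6 × 7 = S + 42 days apart, of which up to 42 days are on the agent.

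**What bounds S**

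There is no upper limit. Two provisions set a lower limit for subjects who stop something after screening:
- Exclusion criterion 13: "Subjects may not take any of the following substances for at least 7 days prior to baseline and throughout the study". The list includes "All dietary or herbal supplements or products", so it can apply to many recruits.
- Medication Washout in Section V: five half-lives plus several days.

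**Other chances to detect a pregnancy before week 6**

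The Subject Visits text gives five scheduled contacts after first dispensing: calls at weeks 1, 2, 4 and 5, and the week 3 visit. The week 1 call and the week 3 visit collect adverse events, and the other three calls check compliance. Subjects can also page a clinician at any hour. Any of these could bring a pregnancy to light, but none includes a test.

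**Expected number newly caught by a baseline test**

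Suppose a urine test detects a pregnancy only after a fixed lag L from conception. The screening test covers conceptions up to (screening − L), and a baseline test covers those up to (baseline − L). The added window is as long as the gap, whatever L is. Hence

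expected number newly caught = N × (rate per 4 weeks) × (gap in weeks ÷ 4).

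Inputs:
- Number dosed: 15, from Background and Significance and from Biostatistical Analysis. Replacement of dropouts (up to 25 recruited, Section V) could raise it somewhat.
- N = 7 women of childbearing potential: assumed.
- Gap of 0 to 4 weeks: assumed.
- Conception rate of 0.5% to 2% per 4 weeks: assumed.

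| Case | Expected number | Chance of at least one |
|---|---|---|
| Gap 0 | 0 | 0 |
| N = 7, 1 week, 0.5% | 7 × 0.005 × 1/4 = 0.009 | not calculated |
| N = 7, 4 weeks, 0.5% | 7 × 0.005 × 4/4 = 0.035 | 1 − 0.995^7 = 0.034 |
| N = 7, 4 weeks, 2% | 7 × 0.02 × 4/4 = 0.14 | 1 − 0.98^7 = 0.132 |
| Ceiling: all 15, 4 weeks, 2% | 15 × 0.02 × 4/4 = 0.30 | 1 − 0.98^15 = 0.261 |

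The expected number scales in proportion to the gap, so an interval longer than 4 weeks would raise these values. They make no deduction for a woman who reports a known or suspected pregnancy at the baseline eligibility check.

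**The case against.** The text and table agree, so this is a design choice and not a contradiction. A pre-dose test exists, a positive result bars participation, and eligibility is confirmed again at baseline, when pregnancy can be asked about. Women who report it then would not be newly caught by a strip, so the counts above are somewhat high for the inputs used. The upper cases also give every woman the full 4-week gap, and the 26% case makes all 15 subjects women of childbearing potential in a study open to both sexes. At mid-range values (2 weeks, 1.25% per 4 weeks) the expected number is 7 × 0.0125 × 2/4 = 0.04. A baseline strip can miss a very early pregnancy, and conceptions just after baseline would still wait until week 6. Finally, the agent is a widely used supplement, and the Background reports no adverse effect on fertility or the fetus and no maternal toxicity in mice at up to 6 g/kg/day.

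Much of this stands: the probability is low, the likely harm is small, and the fix narrows the window without closing it. It does not remove the gap. A woman who does not know that she is pregnant cannot report it. The mouse data are for the calcium salt, and the Background says the authors know of no human studies focused on the effects or safety of magnesium L-threonate itself.

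**Conclusion.** The concern holds. Followed exactly, the plan can dispense the agent to a pregnant woman, in breach of its own exclusion, for up to 42 days before the next scheduled test, unless one of the five intervening contacts or the subject herself reveals the pregnancy first. On the assumed inputs the benefit of a baseline test is about 0 to 0.14 pregnancies newly caught in the whole study, with 0.30 as a ceiling for a 4-week gap in 15 subjects. The number of women, the gap and the conception rate are all assumptions. The 42 days and the absence of a cap on the gap come from the plan. This is a low-probability participant-safety gap that should be closed because closing it costs so little.

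**What to change.** 1. Keep the screening test, so that no pregnant woman goes through a washout.
2. Add a urine pregnancy test at baseline, in the Safety Assessments text and in the pregnancy row of the timeline, and require a negative result before the agent is dispensed.
3. Start the contraception requirement at screening. This reduces the early-pregnancy window that a baseline strip can still miss.

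The cost is one strip of a test already in use, at a visit already held, for each woman of childbearing potential who reaches baseline: about 7 on the assumption used here, about 15 if all dosed subjects were such women. The document changes are one table cell and two wording edits. The downside is an occasional screening work-up wasted when the baseline test is positive.
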